Novel Methods for Ascertainment of Gout Flares - A Pilot Study

Principal Investigators:

[name], MSc (University of Alabama at Birmingham)

[name], MPH (University of Nebraska)

2/10/2017

NCT-X160105005

Summary

Title: Novel Methods for Ascertainment of Gout Flares – A Pilot Study

Duration: 18 months

Study Site(s): University of Alabama at Birmingham (UAB) and University of Nebraska Medical Center (UNMC)

Investigators: [name], MSc; [name], MPH, MSPH; [name], PhD

Methodology: The study is a prospective, randomized, comparison of interactive voice response (IVR) telephone questionnaire/flare reporting system versus RheumPRO (a smartphone study application) with crossover. Adults 18 years and older with gout will be enrolled based on eligibility. Following consent/enrollment individuals will be randomized to either start using an interactive voice response telephone or RheumPRO weekly to track their gout flare status for a period of 12 weeks—Phase 1. At the conclusion of 12 weeks individuals will “crossover” to the opposite study arm and continue for 12 weeks using the opposite mode to report their flare frequency/intensity (i.e., those randomized to IVR for the first phase will use the RheumPRO application in the second phase and vice-versa).

List Abbreviations, Tables, and Figures

Abbreviations :

IVR (Interactive Voice Response)

UAB (University of Alabama at Birmingham)

UNMC (University of Nebraska Medical Center)

Tables:

Table1: Study Visits and Evaluation

Figures:

Figure 1: Study Workflow

1 Contents

1. Study Overview.....	1
1.1 A. Background	1
2 Study Organization and Responsibilities	2
2.1 Study Roster	2
2.2 Study Center.....	3
3 Training Plan	4
4 Communications plan.....	4
5 Recruitment and Retention Plan	5
5.1 Recruitment Plan.....	5
5.2 Participant Retention	5
6 Eligibility criteria	5
7 Informed Consent and HIPAA.....	6
7.1 Overview of the Informed consent document.....	6
7.2 HIPAA Authorization.....	7
8 Study Supplies.....	7
9 Randomization.....	7
10 Study Intervention	7
10.1 Overview	7
10.2 Participant Evaluations- Study timeline, visits, and procedures.....	1
10.2.1 Visit 1.....	1
10.2.2 Visits 2-12.....	11
10.2.3 Visit 13 (Crossover Visit)	11
10.2.4 Visits 14-26.....	18
10.2.5 Unscheduled Visit (IVR/RheumPRO report initiated by patient)	18
11 Data Collection, Study Forms, and Logs	18
11.1 Study Participant Forms	19

11.2	Study Specific Administrative Forms, Logs, and Data Tables.....	19
12	Data Management	20

1.1 A. Background

Acute gout flares are a major cause of morbidity. Flares lead to substantial reductions in health-related quality of life, increased work absenteeism, productivity loss, and substantial healthcare costs. For instance, our group has shown that gout, likely related to acute flares, leads to more than 174,000 emergency department visits in the U.S. annually with corresponding charges approaching \$166 million (1).

In recent surveys conducted by our group, gout patients and healthcare providers alike identified the reduction of gout flares as the highest priority outcome that should be examined in future comparative effectiveness studies of urate lowering therapy (ULT) (unpublished results). Despite consensus about the importance of capturing flares, clinical trials investigating ULTs (2-6) or anti-inflammatory prophylaxis (7) have used inconsistent flare definitions and methods of flare ascertainment. The inconsistency has likely been driven by the absence of a standardized definition or ascertainment method. These deficits limit comparisons that can be made across investigations.

Recently, a group supported by the American College of Rheumatology & European League Against Rheumatism (ACR & EULAR) has attempted to define a gout flare (8-10). For simplicity, the group focused on defining only those flares occurring after a definitive gout diagnosis. Nine elements of a flare definition emerged from the first two studies (8, 9). These nine elements included physician reported information, laboratory data and patient self-report. In a third study, Gaffo et al. compared the discriminatory ability of the self-reported items against the gold standard of a rheumatologist's judgment of flare presence (10). Self-report of 4 criteria had the greatest discriminatory ability with an area under the curve (AUC) of 0.931 (10). These promising results indicate the important role for a standardized self-report definition of a gout flare.

In addition to variability in gout flare definitions, the optimal method for obtaining self-reported flares remains undefined. An early study of febuxostat, for example, assessed flares weekly at physician visits (2). Another study counted a flare only when it was treated by a healthcare provider (4). Still other studies assessed flares during physician visits occurring at variable time points (3, 6). These inconsistent methods also pose practical limitations given by their time and resource intensive nature. Opportunities to increase efficiency have only recently become available with the validation of the self-reported definition for gout flares described above. Self-report can now be combined with technological advances in remote data collection to develop novel and highly efficient methods to identify gout flares. This study will address a pressing need by leveraging technological advances that facilitate the remote and real-time collection of patient reported outcomes (PROs) in gout.

2 Study Organization and Responsibilities

2.2 Study Center

Since this is a study, sites will be monitored by the PIs at each respective site (UAB or University of Nebraska Medical Center (UNMC) according to established monitoring standard operating procedures (SOPs). Study site PIs will oversee the study to assure satisfactory data recording, adherence to the study protocol, Good Clinical Practice (GCP), and study medication accounting. UAB and the UNMC will monitor recruitment utilizing automated reports generated from the study database. UAB and UNMC investigators and staff will have meetings bi-weekly to monitor site recruitment and to determine any intervention for poor recruitment. The staff listed in the study roster will be responsible for all aspects of the trial. This includes but is not limited to the following:

- Finalizing the study protocol
- Development of the manual of procedures and its maintenance
- Participant randomization
- Development and implementation of the data flow and data tracking
- Development of procedures for data entry, error identification, and error correction
- AE monitoring and reporting
- Quality control procedures
- Submitting for IRB review and approval
- Creating reports - enrollment, AEs, participant status (e.g., withdrawals)
- Preparing and sending required reports to the Safety Officer and the IRB
- Submitting all required reports to the study appointed Safety Officer.
- Distribution of all changes, updates and policies of above mentioned reports and documents to the study appointed Safety Officer.
- Maintaining the study binder (regulatory and clinical documents)
- Preparation of all study materials- data tables, recruitment materials, official reports
- Identifying, recruiting, screening, and enrolling participants
- Obtaining IC from each participant
- Protecting participants' rights
- Collecting study data and following participants through study completion

- Compliance and accountability of administration of study intervention
- Communicating questions, concerns, and/or observations to the PIs

All of the above activities will be carried out by the study's project coordinators, project managers, and research assistants on a weekly basis (or more frequently as needed) and monitored by the principal and co-investigators.

In the event a problem is identified by either study site PI or staff, a teleconference/webinar will be scheduled to review the issue. These teleconferences/webinars will include discussions of overall recruitment status and identified barriers to recruitment experienced by the site with the study team. Detailed recruitment issues and suggestions will be discussed, as well as identified barriers.

The study will be conducted under the auspices of the IRBs at UAB and the UNMC. Prior to initiation of the study, the investigator will forward copies of the protocol, Investigator's curriculum vitae (if applicable), study advertisements (if applicable), and all other subject-related documents to be used for the study to the IRB for its review and approval. Before initiating a study, the site PI will have written and dated full approval from the responsible IRB for the protocol. The investigators will also promptly report to the IRB all changes in the study, all unanticipated problems involving risks to human subjects or others, and any protocol deviations, to eliminate immediate hazards to subjects.

3 Training Plan

Each study staff member will be trained in the protocol by the investigators named above. The investigators and all staff involved in the study will have completed their required IRB / human participants training. New study staff members will be trained on the protocol and spend a visit shadowing another trained staff member before carrying out visits on their own.

Prior to conducting visits, the investigator will be asked to sign off that the staff member has been appropriately trained in the study protocol. Training and delegation of responsibility will be documented in the Study training Log (Tab 4.2) and entered into the study binder.

If a staff performance problem arises, several steps will be taken to resolve the problem. First, the project manager will communicate the problem to the PIs. At this stage, the PIs will work with study personnel to identify causes of the problem and offer solutions. If the problem continues, additional training will be considered. In cases of problems of sufficient severity or intractable problems that are not resolved by the procedures described above, the under-performing team member may be removed from active participation in the study.

4 Communications plan

As this protocol is currently only being carried out at two sites (the UAB and UNMC, meetings will be held between the entire study staff every two weeks to communicate the on-going progress of the study.

Topics of discussion at each meeting will include:

- Recruitment progress
- Technology issues or concerns with the study and possible solutions
- Any data issues to be resolved at that time
- Adverse events Safety reporting
- Other study updates

Additionally, study personnel will keep investigators informed of the weekly progress of the study with weekly study work group meetings and email updates that include the following information:

- Number of patients screened that week
- Number of patient visits overall
- Prospective study participants to speak with the following week
- A recap of any adverse events (which would have already been reported immediately following the event)
- Other study updates
- Any recent data collection that is useful for viewing or necessary to see for safety monitoring

5 Recruitment and Retention Plan

5.1 Recruitment Plan

The target population to be recruited is patients with gout. Patients will be recruited from the UAB gout clinic, The Kirklin Clinic, and the UNMC gout clinic. The inclusion and exclusion criteria will be reviewed (and if the participant wishes to proceed, then informed consent will be obtained by the principal investigator, one of the co-investigators, or a trained member of the study staff. Study procedures will not begin until signed informed consent has been obtained.

5.2 Participant Retention

To encourage adherence to the assigned study arm participants will be contacted 2 weeks after enrollment. Study coordinators will inquire about any challenges encountered (eg. technology issues—Fitbit not syncing, trouble logging in to the IRV/RheumPRO app). In addition, participant progress will be monitored on a weekly basis by UAB to ensure participants are completing their assigned weekly flare surveys. If any data from the participant is missing on the Fitbit, the study team will contact them to ensure they know how to charge their devices and are using it appropriately.

6 Eligibility criteria

No subject will be excluded based upon gender or race/ethnicity. All participants must meet the following criteria to be enrolled:

- \geq to 18 yrs. of age with Current physician diagnosed gout
- current hyperuricemia defined as serum urate level >6.8 mg/dl
 - Or if it has been >3 months since their last urate OR they have had an increase in ULT (or change in medication) in the past 3 months then a new urate of ≥ 6.0 must be documented to satisfy inclusion criteria.
- self-report of at least two gout flares in the previous 6 months

- Current smartphone user utilizing a FitBit compatible smart phone (with the ability to download RheumPRO from web link).

7 Informed Consent and HIPAA

7.1 Overview of the Informed consent document

The process of informed consent will be carried out by one of the study physicians in conjunction with the study coordinator and the research assistant involved in the screening visit after the participant appears to meet the pre-screening criteria. During this process, individuals will be informed of all aspects of the study so that they can make an informed decision. Participants will then confirm their willingness to participate in the research study by signing the Informed Consent form (see Tab 2.2 for the complete informed consent). After the participant has signed the consent form, the Principal Investigator and/or the research coordinator conducting the visit must sign and date the Informed Consent Document.

The informed consent document contains the following:

- Disclosure of relevant information to prospective participants about the research;
- The participant's comprehension of the information;
- The participant's voluntary agreement to participate in a research study without coercion or undue influence.
- Complete disclosure of any appropriate alternative procedures and their risks and benefits
- Disclosure of the extent of confidentiality that will be maintained
- Statement of compensation and/or medical treatment available if injury occurs
- Name, address, and telephone number of the Principal Investigator

By signing the consent form, the participant authorizes the use of their personally identifiable information and personal health information, that they understand the study and its benefits and risks, and agree to all other aspects of the study outlined in the form. Participants can withdraw their consent at any time.

If there is a change in any of the study procedures that may affect the participant, the informed consent document will be revised and approved by the IRB. Any participants enrolled in the study prior to a change in procedures will sign the amended consent form. Per NIH policy, the signed consent forms will be kept as part of the study record for at least 7 years after completion of the study.

Important Steps for the Study Staff:

- Provide participants with adequate information concerning the study procedures and scope
- Provide adequate opportunity for the participant to consider all available options
- Respond to the participant's questions and concerns
- Ensure that each participant understands all information provided
- Obtain the participant's written voluntary consent to participate
- Sign the consent form as witnesses
- Provide participants with a copy of the consent form

- Keep the signed form in the participant's binder

7.2 HIPAA Authorization

The privacy requirements, as outlined by The Health Insurance Portability & Accountability Act (HIPAA) to protect the participant's confidentiality, are met by reading through the consent form with the potential study participant before obtaining a signature. Additionally, the following HIPAA Specific requirements are met in the last section of the consent form:

The form contains language that satisfies the HIPAA requirements and outline the protection of health information utilized in the study. That participants are authorizing investigators, IRBs, research administrators, and others to share and disclose their Protected Health Information (PHI) for research purposes.

8 Study Supplies

Each participant will be supplied with a FitBit Charge HR wearable activity tracker. Fitbit will be supplied by UAB to 45 participants along with study binder.

9 Randomization

Randomization will occur by using a random number generator. Specifically, permuted block randomization will be used for balance between cross-over arms throughout the investigation. The study coordinator will maintain the master list and securely store the randomization files. Upon completion of the informed consent and screening CRFs, the RheumPRO application will automatically create a unique study ID. The study coordinator will initiate the randomization procedure after a subject has consented. If any concerns arise during the randomization procedures, the study coordinator will contact the study statistician.

10 Study Intervention

10.1 Overview

At enrollment a questionnaire will be completed by all participants to capture demographics, gout-specific disease history, type of phone used. If participants meet I/E criteria (see Tab 1.1) they will be offered consent for the study (see Tab 2.2).

RheumPPO is a mobile smartphone application developed by UAB to capture Patient Reported Outcomes and data from electronic health trackers like Fitbit. Installation of RheumPRO is required for all participants to ensure that passive data can be collected from study provided Fitbit (<https://www.fitbit.com/>) that will be provided to all enrolled participants (see below). We are exploring the use of passively collected FitBit data to see if more timely prompts to patients regarding gout flares can be determined. Passively collected data will include: steps, distances, heart rate, floors, minutes at various activity levels, and sleep parameters.

Phase 1:

After consenting to participate in the study participants will be randomized to start with the IVR or RheumPRO intervention (Phase 1) groups. Frequency and questionnaire prompts for each system will be matched.

The IVR system includes tailored scripting of Gout Flare and Patient Reported Outcome questions (with skip logic), recorded by a member of the research team. The system will automatically dial participants at a schedule time (eg. Monday 4 PM) and if no answer will attempt 2 more times at the same time over the following 2 days (eg. Tuesday 4 PM, Wednesday 4 PM). Participants will self-navigate through the questions using their telephone keypad. Participants can also call into the system to complete surveys if they experience a flare on a day they are not scheduled to receive a call. The IVR system will be programmed to call the patient weekly for 12 weeks to complete a weekly Gout Flare Survey. Consistent with the published gout flare self-report definition, gout flare ascertainment questions will include whether the recent flare is similar to past flares, the number of swollen joints and the number of warm joints. Pain at rest during the attack will be assessed on a 0-9 scale. Together, these questions attain 90% accuracy with physician-diagnosed gout. Further questions will include peak pain, timing of attack and duration of attack if completed. We will capture patient reported outcome measures (e.g. pain, fatigue, sleep) using instruments from the NIH PROMIS assessment center (<https://www.assessmentcenter.net/>). In addition IVR questionnaires at months 1, 3, and 6 will assess IVR ease of use, burden of use, willingness to continue use and disruption to daily activities. At enrollment the study coordinator will explain how the IVR works, planned survey schedule, and that participant -initiated calls to IVR are allowed.

Participants randomized in Phase 1 to the RheumPRO application will complete the exact same Gout Flare Survey questions as the participants randomized to the IVR group, but will complete them using the RheumPRO application that will be downloaded on their smartphone. The RheumPRO application will be programmed to notify participants weekly for 26 12 weeks via a scheduled (eg. Monday 4 PM) “pop-up” to complete Gout Flare and Patient Reported Outcomes Surveys. Participants self-navigate through the survey questions using their smartphone. If participants do not complete the Gout Flare RheumPRO will generate 2 more “pop-ups” at the same time over the following 2 days (eg. Tuesday 4 PM, Wednesday 4 PM). Participants can also open the RheumPRO application on their smartphone and complete surveys or if they experience a flare on a day they are not scheduled to complete a survey. In addition, RheumPRO questionnaires at months 1, 3, and 6 will assess RheumPRO ease of use, burden of use, willingness to continue use and disruption to daily activities. At enrollment the study coordinator will explain how RheumPRO works, planned survey schedule, and that participant -initiated surveys in RheumPRO are allowed.

Phase 2:

At the conclusion of 12 weeks individuals will “crossover” to the opposite study arm and will continue in the study for an additional 12 weeks using the opposite technology to report their flare frequency/intensity (i.e., those randomized to IVR for the first phase will use the RheumPRO app in the second phase and vice-versa) completing the exact same Gout Flare and Patient Reported Outcome questions as were completed in Phase 1. Activities to be completed at each study visit are detailed below.

Figure 1. Study Workflow

[figure not shown]

Table 1. Study Visits and Evaluation

[figure not shown]
	1	2	3	4	5	6	7	8	9	10	11	12	13	14	15	16	17	18	19	20	21	22	23	24	
Informed Consent	X																								
Paper Screening	X																								
Paper Enrollment	X																								
IVR/RheumPRO Initial Flare Assessment	X																								
Patient- Weekly Flare Assessment*		X	X	X	X	X	X	X	X	X	X	X	X	X	X	X	X	X	X	X	X	X	X	X	X
2 week adherence call		X																							
1-month follow-up Assessment and phone check-in				X																					
3-month follow-up Assessment												X													
Crossover Study Visit†													X												
1-month follow-up Assessment and phone check-in																		X							
6-Month follow-up Assessment																									X
Unscheduled Patient Initiated Flare Assessment																									

*Weekly flare assessment are completed by patient using IVR or RheumPRO application; †Crossover visit will be conducted in person at the study site.

[figure not shown]

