10.2.2 Visits 2-12

- Visits 2-12 will be completed by participant using IVR or RheumPRO application
- Participants will receive notification the day of, 24 hours, and 48 hours later
 - IVR will call participant at designated time to complete
 - RheumPRO will send push notifications participants to complete survey

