10.2.4 Visits 14-26

- Phone IVR/RheumPRO Visit by patient
- Participants will receive notification the day of, 24 hours, and 48 hours later
 - IVR will call at designated intervals to complete
 - RheumPRO will send push notification to complete survey

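### Section 10.1 says prompts will be matched, but the stated retry trigger is an unanswered call for IVR and an unfinished survey for RheumPRO; one completion-based rule should cover both

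*Combined protocol and SAP*

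**What the plan says.** Section 10.1 (Overview) makes the general commitment under Phase 1: "Frequency and questionnaire prompts for each system will be matched". It then describes each system.

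- **IVR:** the system dials at the scheduled time and "if no answer will attempt 2 more times at the same time over the following 2 days". What counts as no answer is not defined.
- **RheumPRO:** "If participants do not complete the Gout Flare RheumPRO will generate 2 more" pop-ups, also at the same clock time on the next two days.

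Section 10.1 ends by pointing forward: "Activities to be completed at each study visit are detailed below". Section 10.2.2 (Visits 2-12) then says, for both systems, "Participants will receive notification the day of, 24 hours, and 48 hours later", and adds that "IVR will call participant at designated time to complete". Section 10.2.4 (Visits 14-26) repeats the notification sentence and says "IVR will call at designated intervals to complete". Neither section states a condition for the second and third notices.

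Other provisions bear on unfinished surveys:

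- **Section 10.1:** "Participants can also call into the system to complete surveys if they experience a flare" on an unscheduled day. The same paragraph ends by saying, without mentioning a flare, that calls started by the participant are permitted. Section 10.2.5.2 describes the unscheduled call as a way to report a flare.
- **Section 5.2:** UAB monitors completion of the weekly surveys each week, and coordinators contact participants two weeks after enrollment about difficulties.
- **Table 1:** a 1-month phone check-in in each phase.

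**The concern.** The Summary describes the study as a randomized comparison of two reporting systems, so the prompting rule should be the same in both. Otherwise a difference in response may reflect how often people were reminded and not how they were asked to report. Here the two retry conditions in 10.1 treat the same lapse differently. A participant who picks up the phone and hangs up halfway has answered. A participant who opens the app and stops halfway has not completed.

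The 2-by-2 crossover does not protect against this. It balances participant and period effects between the systems, but the trigger belongs to the system and moves with it. A difference in trigger is therefore fully confounded with mode in each period and each sequence. At stake is the reading of any RheumPRO versus IVR contrast in weekly response or in flares captured.

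**Working it through.** **Step 1. Set the three descriptions side by side.**

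| Feature | IVR, 10.1 | RheumPRO, 10.1 | Both, 10.2.2 and 10.2.4 |
|---|---|---|---|
| First prompt | weekly, scheduled time | weekly, scheduled time | day of |
| Further prompts | 2 | 2 | 2 (24 h and 48 h) |
| Timing | same time, next 2 days | same time, next 2 days | 24 h and 48 h |
| Trigger | call not answered | survey not completed | none stated |

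Only the last row differs. Read literally, the third column would prompt people who have already finished, which neither condition in 10.1 does. If a condition is implied there, the only ones on offer are the two unequal ones in 10.1. So 10.2 does not settle the trigger.

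**Step 2. Follow one week in which the first prompt is taken up but the survey is not finished.** On the literal reading of 10.1, IVR gives 1 prompt in total and RheumPRO gives up to 1 + 2 = 3.

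**Step 3. Bound and illustrate the loss within IVR.** The plan gives no completion figure to reproduce. The comparison is IVR as written against IVR with a completion trigger, so nothing is assumed about RheumPRO. Let a be the chance that a call is answered and c the chance that an answered call is finished, with up to 3 independent attempts. Both a and c are assumptions; the documents give neither.

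- As written, read literally: c(1 − (1 − a)³)
- With a completion trigger: 1 − (1 − ac)³
- Upper bound on the loss, the weeks that end in an answered but unfinished call: u = (1 − c)(1 − (1 − a)³)

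Example with a = 0.5, c = 0.95. As written: 0.95 × 0.875 = 0.831. Completion trigger: 1 − 0.525³ = 0.855. Loss: 2.4 points. Bound: 0.05 × 0.875 = 4.4 points.

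| c (assumed) | Loss, a = 0.5 to 0.9 | Bound u, a = 0.5 to 0.9 | Loss if a survey once left unfinished is half as likely to be finished on retry |
|---|---|---|---|
| 1 | 0 | 0 | 0 |
| 0.99 | 0.5 to 1.0 | 0.9 to 1.0 | 0.3 to 0.7 |
| 0.95 | 2.4 to 4.8 | 4.4 to 5.0 | 1.3 to 3.2 |
| 0.80 | 8.4 to 17.9 | 17.5 to 20.0 | 4.6 to 11.3 |

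Entries from the second column on are percentage points of weekly IVR completion. The last column replaces c by c/2 after an unfinished call: the loss is a(1 − c)[1 − (1 − ac/2)²] + (1 − a)a(1 − c)(ac/2). For a = 0.5, c = 0.80 this is 0.1 × 0.36 + 0.05 × 0.2 = 0.046.

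The table shows how the loss depends on the rate of unfinished calls. It does not estimate that rate.

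**The case against.** The strongest reply is that the design is already matched. Frequency, number of retries, clock time and survey content agree across systems, and the matching sentence in 10.1 does not mention triggers. The visit sections, to which 10.1 defers for detail, give one schedule for both. A pop-up has no answered state, so each sentence may simply use the language natural to its medium, and the IVR programmer may treat an abandoned call as unanswered. All of this is plausible, and on any of these readings the effect is zero. It does not close the point, because the visit sections state no condition and do not say that they override 10.1.

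The second reply is that other safeguards exist. Weekly monitoring in 5.2 is aimed at completion in either mode, the 2-week contact and the 1-month check-ins can bring problems to light, and 10.1 permits participant-initiated IVR calls in general terms. These may offset part of any loss and deserve weight. But 5.2 names no action for an unfinished survey, the 2-week contact is timed from enrollment and so falls in the first phase, and the call-in route is otherwise described for reporting a flare. None is a stated retry for an unfinished weekly survey that matches RheumPRO's.

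The third reply is that Section 13 describes a feasibility pilot and names no completion or flare-capture endpoint; its between-system tests directly follow the sentence on preference and satisfaction surveys. This stands and limits the importance of the point.

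A reader might infer that the plan deliberately prompts IVR users less, that they cannot finish an interrupted survey, or that the Section 13 comparisons are biased. The documents support none of these. They show an unreconciled wording that would produce unequal prompting only under one way of programming it.

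**Conclusion.** The retry triggers in 10.1 differ by system, and 10.2.2 and 10.2.4 do not resolve which applies. That much is certain from the text. Whether it affects the data depends on how the IVR redial is programmed and how often answered calls are left unfinished, and the documents give neither.

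If every answered call is finished, if an incomplete call counts as unanswered, or if all three notices go out in both modes, there is no effect. On the literal reading, IVR weekly completion could be reduced by at most the share of weeks that end in an answered but unfinished call: at most 1, 5 or 20 points if that share is 1%, 5% or 20%, all assumed. The larger figures need high rates of abandoned calls for which there is no evidence, so they should not drive the rating. With no named endpoint at risk and partial safeguards in place, the point is minor. It is still worth correcting, because a mode-linked difference in prompting could not be separated from mode in the analysis.

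**What to change.** In Sections 10.1, 10.2.2 and 10.2.4, state one retry rule for both systems: re-prompt at 24 and 48 hours unless that week's survey is complete. Define complete (for example, all required items reached under the skip logic), and say how hang-ups and voicemail pick-ups are treated. Program the IVR redial on the same basis.

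The cost is aligned wording in three sections and, where the IVR system can detect an unfinished survey, a change to its redial setting. The downside is a few extra calls to participants who answered but did not finish.

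The documents do not say whether the IVR system can detect an incomplete survey. If it cannot, an optional fallback is to log the outcome of every attempt in both systems and report first-prompt completion by mode as a descriptive summary.
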